Study procedure visit: Participants will be reminded by phone call or email 48 hours before the study visit to withdraw from medications affecting urination per our inclusion criteria. On the day of the visit, participants will sign and date the informed consent document and complete a compensation form, LURN SI-29 questionnaire survey, and demographics questionnaire survey. Pre-procedure vital signs, point of care urinalysis, and a pregnancy test will be obtained. Participants will be excluded with a positive pregnancy test or delayed until resolution of infection with a positive urinalysis (per exclusion criteria). If participants have negative urinalysis, negative pregnancy test, and meet inclusion/exclusion criteria they will undergo current perception threshold (CPT) testing in the bladder and urethra.

Participants will be assigned to the intervention arm based on CPT. CPT data will be analyzed immediately by percentage change against normative data to stratify investigational allocation to intravesical (bladder) electrical stimulation or intraurethral electrical stimulation (Kenton et al. 2007). The allocation will be as follows: 1) if percentage change of urethral CPT > percentage change of bladder CPT then participants will receive intraurethral electrical stimulation, 2) if percentage change of bladder CPT > percentage change of

urethral CPT then participants will receive intravesical electrical stimulation, or 3) if percentage change of urethral CPT = percentage change of bladder CPT then participants will receive intravesical stimulation when cystometry "first desire to void" > 275ml or intraurethral stimulation when pressure-flow detrusor pressure at maximum flow < 30 cmH2O and maximum flow < 10 ml/s. After the investigational session of stimulation, participants will undergo post-study urodynamic studies which will include cystometry and pressure-flow studies. At the completion of these procedures, participants will be given standard urogynecology post urodynamic study instructions. They will also be instructed to complete remotely a post-study condition LURN SI-29 questionnaire that will be emailed via RedCap 7 days after the study visit. At that time, they will be considered to have completed the study.

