The potential benefits of the proposed study to research participants are as follows:

- Participants will experience standard procedural risks involved with invasive urodynamics and electrical stimulation. The potential acute benefit of decreased lower urinary tract symptoms (LUTS) and increased bladder emptying is reasonable relative to the risks of additional urodynamic testing that they may have otherwise undergone.

The potential risks for the study are as follows:

- The risk for breach of confidentiality of personally identifiable information. There is minimal risk given our Data and Safety Monitoring Plan but this risk will result in loss of confidentiality of study participation.
- Risk for breach of confidentiality with electronic informed consent. Participants will receive a signed copy of their consent via the email address they provide and this risk is disclosed in the informed consent form.
- Participants will be asked to withdraw medications (e.g., alpha-adrenergic antagonists, cholinergic agonists, cholinesterase inhibitors) that affect urination for 48 hours prior to study participation. This will create a risk of them being untreated for the medicated condition. We do not expect significant complications other than decreased quality of life from 48 hours of medication withdrawal. We will protect against the risk of significant adverse events during medication withdrawal by instructing participants to contact study personnel in the event of adverse effects.
- During invasive urodynamic testing, there is a risk of irritation and infection with catheterization. Participants may develop a urinary tract infection, hematuria, or pain and discomfort. We will minimize the risk of urethral irritation by lubricating the catheter with K-Y jelly and having the fewest de novo catheterizations possible Additionally, we will minimize the risk of infection by using sterile preparation techniques, as well as antiseptic cleaning of the working area.

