- There is a risk of painful sensations from electrical stimulation to the bladder and urethra. Participants can elect to decrease or terminate stimulation at any point during the study. We will minimize the risk of activating nerve fibers carrying painful stimuli by individually adjusting current amplitude to 80% of their maximum tolerable intensity. Every subject will be titrated down from a stimulation parameter that they feel is uncomfortable. The stimulation amplitude will be guided by the values obtained from the Current Perception Threshold forced choice paradigm, where a baseline intensity alignment automatically increases amplitude until the participant reports detection. Participants will be informed of any sensations they may perceive as unpleasant and may elect to terminate stimulation at any point.
- Participating in this study while pregnant may expose the unborn child to unknown risks. There is no risk level because we have excluded pregnant women.

- There may be some unknown and unforeseeable risks related to the study. Participants will be informed of any significant new information learned during the study that might cause them to change their mind about participating in the study. Significant new findings developed during the research, which may relate to their willingness to participate will also be provided to them.

Costs to the Subject

• Describe and justify any costs that the subject will incur as a result of participation; ordinarily, subjects should not be expected to pay for research without receiving direct benefit.

There will be no cost to the subject as a result of the participation.

Data Analysis & Statistical Considerations

Describe endpoints and power calculations. Provide a detailed description of how study data will be
analyzed, including statistical methods used, and how ineligible subjects will be handled and which
subjects will be included for analysis. Include planned sample size justification. Provide estimated time
to target accrual and accrual rate. Describe interim analysis including plans to stop accrual during
monitoring. Phase I studies, include dose escalation schema and criteria for dose escalation with
definition of MTD and DLT.

Expected enrollment n = 20 neurologically-intact women with underactive bladder **Expected effect size** (dz) = 0.67 **Power (1 – \beta) =** 0.8

Time to Target Accrual 2 years

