To account for participants failing to meet our eligibility criteria, it is anticipated that a total of 100 adult women will be screened to achieve n=20 total study participants. We expect to screen all patients with ICD codes suggestive of underactive bladder because a DEDUCE query revealed that in 2019 Duke Urogynecology clinics saw 34 patients meeting our criteria and approximately 10 of those patients went on for urodynamic studies. It is our expectation that the lack of consistent terminology and diagnostic parameters for underactive bladder will result in a large patient population failing to meet our eligibility criteria. Our expected enrollment will enable detection of a 7.5% change in voided percentage after stimulation with power (1-beta) of 0.8.

Statistical Methods

Primary Aim 1: Use of intraurethral electrical stimulation or intravesical electrical stimulation to assess increase in voided percentage during pressure-flow studies

Hypothesis: Electrical stimulation will increase voided percentage, and this hypothesis will be evaluated with non-parametric tests.

Method: Data will be analyzed by Wilcoxon signed-rank test to determine the influence of intravesical and intraurethral stimulation on bladder emptying.

Primary Aim 2: Use of LURN SI-29 questionnaire to assess whether electrical stimulation decreases urinary bothersome symptoms and increase bladder sensation during filling and emptying

Hypothesis: Intravesical (bladder) stimulation will decrease affirmatory responses to bothersome urinary symptoms and increase affirmatory responses to sensation during filling and emptying, whereas intraurethral stimulation will decrease affirmatory responses to bothersome symptoms during emptying.

Method: Data will be analyzed by the McNemar Exact Test or the Wilcoxon signed-rank test to determine the influence of intravesical or intraurethral stimulation on sensation.

Secondary Aim 1: Assess bladder or urethral current perception threshold (CPT) in women with underactive bladders

Hypothesis: Women with underactive bladder will have increased bladder CPT and increased urethral CPT (reduced sensory nerve activity) compared to normative data in asymptomatic women, and this hypothesis will be evaluated with the Dunn's multiple comparisons test.

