Participant privacy will be maintained through confidential phone screens and consultation behind closed doors in the Urogynecology Clinic. Participant information will be recorded in their subject binder and stored for six years per Duke protocol. Their electronic personal health information will be behind an enterprise-grade firewall and will not be shared with outside entities unless required by the sponsor.

Research study participants will be given contact information to [name] and will be allowed access during working hours (9am-5pm) to answer questions related to study risks and procedures. To maintain patient safety oversight, [name] will submit Adverse Event reports to an independent safety monitor after 5 participants have been evaluated with the intervention. The independent safety monitor is [name], M.D., a Duke Urogynecologist. We also have a Clinical Quality Management Plan where a Quality Management Reviewer will review all safety events during the review of the participant charts to ensure appropriate reporting according to DUHS IRB policy. If any Serious Adverse Events, Protocol Deviations/Violations, and/or Unanticipated Problem are observed during the review, these will be communicated to the study team promptly. The QM reviewers are [name], [name], or [name]. In addition to the Clinical Quality Management Plan, study staff will review participants' charts 30 days after the study visit to identify safety/adverse events and facilitate timely reporting. All protocol deviations and adverse events will be promptly reported to the Institutional Review Board in accordance with institution and Human Research Protection Program policies. All additional regulatory and monitoring requirements of the Investigational Device Exemptions will be carried out by the study team in accordance with 21 CFR 812.2(b)(1).

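### No adverse-event question is described for the day-7 survey, so infection, hematuria or pain that never reaches a chart may be missed and may enter the Aim 2 endpoint unrecognized

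*Combined protocol and SAP*

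**What the plan says.** The Risk/Benefit Assessment names the harms expected from catheterization: "Participants may develop a urinary tract infection, hematuria, or pain and discomfort". It gives no rates or timing.

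Under Study procedure visit (Design & Procedures), the baseline LURN SI-29 and a urinalysis are done before instrumentation. Afterwards women receive standard post-urodynamic instructions, whose content is not given, and a "post-study condition LURN SI-29 questionnaire that will be emailed via RedCap 7 days after the study visit". The protocol then states: "At that time, they will be considered to have completed the study". No adverse-event question, safety call or later urinalysis is described.

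Under Data & Safety Monitoring, study staff review participants' "charts 30 days after the study visit to identify safety/adverse events and facilitate timely reporting". A quality management reviewer also examines safety events while reviewing participant charts; no date is given. Women have a working-hours contact, described as a route for questions about risks and procedures. Adverse-event reports go to an independent safety monitor after 5 participants, and events must be reported promptly to the IRB.

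For Primary Aim 2 the method reads: "Data will be analyzed by the McNemar Exact Test or the Wilcoxon signed-rank test to determine the influence of intravesical or intraurethral stimulation on sensation". It has no provision for a woman who has an infection or procedure-related pain in the recall week.

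**The concern.** Both scheduled searches see only what someone has written in a chart. A woman who has burning for three days, sees blood once, or is treated for an infection outside the health system has no planned route into the safety data unless she calls. The study does contact every woman on day 7, but is not described as asking her about such events.

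Two things are at stake. One is the adverse-event count that reaches the safety monitor and the IRB. The other is the reading of Primary Aim 2. The baseline form covers the week before instrumentation and the day-7 form covers the week after it. No sham or unstimulated group is described, so the paired change mixes any stimulation effect with any effect of catheterization. Knowing which women had an infection or irritation is the main way to judge how much of a change could be procedural.

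**Working it through.** **1. The plan's own figure, and why it is not in question.** Inputs from Data Analysis & Statistical Considerations: "n = 20 neurologically-intact women with underactive bladder", dz = 0.67, power 0.80. Alpha is not stated; I assume 0.05 two-sided. For a paired t-test the noncentrality is 0.67 × √20 = 3.00, and the noncentral t gives power 0.811 at n = 20, so the stated size is reproduced. It was set for voided percentage ("Our expected enrollment will enable detection of a 7.5% change in voided percentage after stimulation with power (1-beta) of 0.8"; implied SD of the paired difference 7.5/0.67 = 11.2 points). Nothing in this point changes it.

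**2. Time windows side by side.**
- Baseline LURN: completed at the visit before catheterization; the items quoted under Inclusion Criteria recall the preceding 7 days.
- Post-study LURN: sent at day 7. Answered promptly, it recalls roughly the visit to day 7.
- End of participation: day 7. Staff chart review: day 30.

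Procedure-related events in the first week thus fall inside the post-stimulation recall window and outside the baseline one. The day-30 review spans that week, so charted events can be linked to Aim 2 answers; uncharted ones cannot.

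**3. What may be missed (all rates assumed; none is in the documents).** With true event rate r and chart capture c, expected events are 20r, expected recorded events are 20rc, and the chance that none is recorded is (1 − rc)^20.

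| r | Expected events | Recorded at c = 30% to 70% | None recorded, c = 100% | None recorded, c = 70% | None recorded, c = 30% |
|---|---|---|---|---|---|
| 5% | 1 | 0.3 to 0.7 | 36% | 49% | 74% |
| 10% | 2 | 0.6 to 1.4 | 12% | 23% | 54% |
| 15% | 3 | 0.9 to 2.1 | 4% | 11% | 40% |
| 20% | 4 | 1.2 to 2.8 | 1% | 5% | 29% |

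Expected missed events, 20r(1 − c), run from 20 × 0.05 × 0.3 = 0.3 to 20 × 0.20 × 0.7 = 2.8.

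**4. What one to three affected women could do to Aim 2 (illustration).** Exact McNemar, two-sided:
- 6 improved, 0 worsened: 2 × (1/2)^6 = 0.031. One otherwise unchanged woman worsens (6 vs 1): 2 × 8/128 = 0.125.
- 8 vs 1: 2 × 10/512 = 0.039. One more worsens (8 vs 2): 2 × 56/1024 = 0.109.

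Signed-rank test, n = 20, normal differences, with dz = 0.67 borrowed from voided percentage because no LURN effect size is given (3000 simulated runs, two-sided 0.05):

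| Women affected | Each worsens by 1 SD | Each worsens by 2 SD |
|---|---|---|
| 0 | power about 0.79 | power about 0.79 |
| 1 | 0.71 | 0.61 |
| 2 | 0.62 | 0.41 |
| 3 | 0.53 | 0.23 |

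These count affected women whether or not they are charted, assume every event worsens the score, and pool both arms although Aim 2 states different hypotheses by arm. They show sensitivity, not a forecast.

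**5. Direction.** Irritation that raises bother works against the hypothesis in either arm. For the bladder arm, Aim 2 also counts more sensation during filling and emptying as benefit; irritation could raise that too and favor the device.

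**The case against.** The strongest reply is that this is a single-visit pilot of 20 women with an independent safety monitor, quality management review, a day-30 chart review and prompt IRB reporting. Participants come mainly from the same urogynecology clinics, so some after-care may well be charted there. That stands as a limit on importance, but none of these layers asks the woman. The contact line is passive, and the one explicit instruction to report adverse effects concerns the medication withdrawal before the visit.

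Several stronger readings are tempting and are not supported:
- **That the day-30 review is the only route.** The quality management review and the contact line also exist, and the content of the post-urodynamic instructions and the consent form is not available.
- **That the day-7 survey asks nothing relevant.** Only five LURN SI-29 items are quoted. The supportable statement is that no adverse-event question is described with it.
- **That events are undercounted.** No event timing, event rate or capture rate is given, so they may be undercounted.
- **That the bias runs against the device.** It can run either way, as step 5 of the working shows.
- **That nothing exists to check it.** The chart record is incomplete, not absent.
- **That the benefit-risk statement depends on the trial's event count.** That statement is prospective.

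It is also fair to object that dropping women with an infection conditions on something the procedure may have caused, and that someone must read the survey responses. Both are met in the fix.

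**Conclusion.** The point holds in a limited form. Scheduled detection after the visit is chart-based, and the one scheduled contact with every woman is not described as asking about adverse events. Infection, hematuria or pain that stays out of the chart may be missed. When it occurs in the first week it falls inside the Aim 2 recall window, where it could move bother or sensation with only a partial record to check against.

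The size cannot be derived from the documents. Under assumed event rates of 5% to 20% and capture of 30% to 70%, 0.3 to 2.8 events among 20 women would go unrecorded; in the worked McNemar examples a single affected woman moves p across 0.05. This also assumes prompt completion of the survey and that the 7-day recall of the quoted items applies to the items used for Aim 2. The voided-percentage aim and its sample size are unaffected. This is an inexpensive improvement worth making, not a flaw that invalidates the trial.

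**What to change.** - **Survey.** Add a short adverse-event block to the existing day-7 REDCap survey: infection diagnosed or treated and where, blood in urine, pain or burning, inability to urinate, and unplanned care. Record positive answers as adverse events for review by the study team. Keep the day-30 chart review as the second source.
- **End of follow-up.** Reconcile the statement that women have completed the study at day 7 with the day-30 safety review, so that end of participation and end of safety follow-up are each defined.
- **Aim 2.** Keep all women in the primary analysis. Flag those with an event in the recall window and report a supportive analysis without them, labelled as conditioning on a post-procedure event that the procedure itself may cause. If irritation raises bother, that exclusion removes unfavorable outcomes, so it must not replace the main result.

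**Cost.** A slightly longer survey, someone on the existing team to check responses, and a somewhat higher reported event rate. No new visit or procedure is needed. The block makes procedural effects visible; it does not remove them from the paired comparison.
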